4.2.2 Analysis of the Secondary Objectives

Group-level analyses for the secondary mental health and adherence outcome measures will be the same as those used for the primary analysis of the primary outcome measures. The Wilson 3-item scale and log viral load are continuous measures. For viral suppression, which is a dichotomous measure, the first stage of the group-level analyses will involve calculating the proportion with that outcome within each group, and then proceeding as above using paired t-tests.

For the analysis of the secondary safety outcome measure, the number and proportion of youth experiencing at least one safety outcome measure (see Section 3.2) will be summarized by arm with exact 95% confidence intervals (CIs). Differences in proportions between arms will be summarized with an exact 95% CI on the difference. Proportions will also be summarized only including events assessed as related to treatment. The types of safety outcome measures that occur, including social harms, will be summarized.

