### **2.2 Secondary Objectives**

The secondary objectives of this study are to:

- 2.2.1 Determine the feasibility, acceptability, and fidelity of a TI-CBT intervention.
- 2.2.2 Evaluate whether a TI-CBT Intervention is associated with improved depression, anxiety, and/or traumatic stress symptoms for youth living with HIV compared to a Discussion Control following the last group session and at 12 months.
- 2.2.3 Assess whether a TI-CBT Intervention is associated with improved ART adherence (hair samples, self-report) and viral suppression (HIV RNA plasma) for youth living with HIV compared to a Discussion Control following the last group session and at six and 12 months.
- 2.2.4 Assess whether a TI-CBT Intervention is associated with improved structural factors for youth living with HIV (HIV stigma and support for adherence; barriers to adherence; gender-based violence; gender roles) compared to a Discussion Control following the last group session and at six and 12 months.
- 2.2.5 Assess whether a TI-CBT Intervention is associated with improved structural factors for caregivers (HIV knowledge, stigma, and support for adherence; barriers to adherence) compared to a Discussion Control following the last group session and at six and 12 months.
- 2.2.6 Assess whether a TI-CBT Intervention is associated with improved behavioral risk outcomes for youth living with HIV (alcohol/drug use; sex-risk behaviors; caregiver report of youth behavior) compared to a Discussion Control following the last group session and at six and 12 months.
- 2.2.7 Identify the individual, social, and structural barriers, and facilitators to implementation of a TI-CBT Intervention.
- 2.2.8 Compare the rates of all targeted adverse events between a TI-CBT Intervention and a Discussion Control for youth living with HIV.

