### **12.5.2 Unimproved Mental Health or Clinical Deterioration**

Continued or worsening of mental health symptoms is always a risk regardless of use of counseling. In addition, as suicidal ideation is a symptom of depression, suicide or suicide attempt is a risk. Clinical deterioration due to the underlying psychiatric condition(s), or the study intervention (TI-CBT), is also a risk.

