3.2 Secondary Outcome Measures

The secondary outcome measures used to address the secondary objectives listed in Section 2.3 are as follows.

Mental Health Measures

The secondary mental health measures will be the same measures as in Section 3.1 above but assessed at the immediate post-last group session (IPL).

ART Adherence Measures

The following ART adherence measures will be assessed at the IPL and at 6 months:

1. Wilson 3-item scale (self-report);
2. Viral load (HIV-1 RNA copies/mL).

Note: Hair samples will be tested following the 12-month visit, and will not be available for the primary analysis report or primary manuscript.

Safety Measures

The outcome measures for safety are the following youth adverse events:

1. Grade 2 or higher suicidal ideation or attempts;
2. Grade 3 or higher psychiatric disorder;
3. Grade 3 or higher insomnia.

4 Statistical Principles

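### The only safety contrast in the SAP with an estimated difference and confidence interval pools suicidal events with psychiatric disorder and insomnia; each event type should have its own.

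*SAP*

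**What the plan says.** Protocol 2.2, objective 2.2.8, is to "Compare the rates of all targeted adverse events between a TI-CBT Intervention and a Discussion Control for youth living with HIV". SAP 2.3.2 repeats it.

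SAP 3.2 lists three numbered safety measures: "Grade 2 or higher suicidal ideation or attempts", "Grade 3 or higher psychiatric disorder" and "Grade 3 or higher insomnia". Protocol Table 4 lists the same three separately.

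SAP 4.2.2 then treats them as one measure: "the number and proportion of youth experiencing at least one safety outcome measure (see Section 3.2) will be summarized by arm", with exact 95% CIs. It continues: "Differences in proportions between arms will be summarized with an exact 95% CI on the difference". A further version of the proportions counts only treatment-related events. For the separate types it says: "The types of safety outcome measures that occur, including social harms, will be summarized".

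SAP 5.2.5 asks for a by-arm summary of all new reportable adverse events after entry, and its note names the three categories. It specifies no difference or interval for them.

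**The concern.** The objective speaks of all targeted adverse events, and three measures are defined, but only their union gets an estimated contrast. The three are unequal. Suicidal events enter at grade 2 and the other two at grade 3, and a youth with grade 3 insomnia counts the same as one who attempted suicide.

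Protocol 12.5.2 names the most serious harm, saying that "suicide or suicide attempt is a risk", and it also lists deterioration due to TI-CBT as a risk. Youth are enrolled for moderate to severe symptoms, so background psychiatric events in both arms are plausible. Such events dilute a contrast confined to suicidal events. The report could then show more suicidal events in one arm, give no estimate of that difference, and carry a pooled interval that includes zero. Attempts are not separated from ideation in any estimated contrast.

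**Working it through.** **The plan's own figure.** There is none to reproduce. The documents give no event rate and no precision target for safety; protocol Table 5 concerns the mental health scores only.

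**Inputs.** Arm size is 96 to 128 youth (SAP 2.1). All event rates below are assumptions. Let s be the proportion with a suicidal event and q the proportion with another targeted event, independent of s. Youth are treated as independent.

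**Step 1: what pooling does to the contrast.** The pooled proportion is p = 1 − (1 − s)(1 − q). Take s = 3% versus 10%, and q = 20% in both arms.

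- Pooled: 1 − 0.97 × 0.80 = 22.4%, and 1 − 0.90 × 0.80 = 28.0%.
- The difference falls from 7.0 to 5.6 points, that is, by the factor 1 − q.
- The variance term Σp(1 − p) rises from 0.03 × 0.97 + 0.10 × 0.90 = 0.119 to 0.224 × 0.776 + 0.280 × 0.720 = 0.375.
- At 96 per arm the standard error is √(0.119/96) = 3.5 points alone and √(0.375/96) = 6.3 points pooled. Difference over standard error drops from about 2.0 to 0.9.

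**Step 2: how often a 95% interval excludes zero.** The binomial outcomes were enumerated in full, using the Newcombe interval. With Wilson limits (l, u) in each arm and d = p₁ − p₂, the lower limit is d − √[(p₁ − l₁)² + (u₂ − p₂)²] and the upper limit is d + √[(u₁ − p₁)² + (p₂ − l₂)²]. Suicidal events are 3% versus 10% throughout.

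| Measure | 96 per arm | 128 per arm |
|---|---|---|
| Suicidal events alone | 47% | 62% |
| Pooled, other events 2% in both arms | 38% | 50% |
| Pooled, other events 5% in both arms | 30% | 39% |
| Pooled, other events 10% in both arms | 22% | 28% |
| Pooled, other events 20% in both arms | 15% | 18% |
| Pooled, other events also rise, 10% versus 17% | 61% | 74% |

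In the last row the pooled proportions are 1 − 0.97 × 0.90 = 12.7% and 1 − 0.90 × 0.83 = 25.3%.

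**Step 3: one concrete table, 96 per arm.**

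- Suicidal events in 10 versus 2 youth: difference 8/96 = 8.3 points, 95% CI 1.4 to 16.2.
- Pooled, 24 versus 17 youth: difference 7/96 = 7.3 points, 95% CI −4.4 to 18.7.
- Youth with other events only number 24 − 10 = 14 and 17 − 2 = 15. A nearly equal background is therefore enough; no opposite imbalance is needed.

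**Step 4: attempts alone.** At an assumed 1% versus 4%, the interval excludes zero in 17% (96 per arm) to 27% (128 per arm) of trials.

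**Limits of the check.** The exact interval named in the SAP would generally be somewhat wider than Newcombe's. Allowing for correlation within groups would widen the intervals further, for the pooled and single measures alike.

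**The case against.** The case on the other side has real weight.

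- A reader might infer that the pooled measure is the only safety comparison between arms. It is not: SAP 5.2.5 summarizes reportable adverse events by arm and lists deaths with arm and cause. What is missing is an estimated difference with an interval for each type.
- A reader might infer that repeat events are lost. They drop out of the youth-level proportion only; the 5.2.5 summary covers all new events.
- A reader might infer that the trial could formally conclude there is no difference in harm. SAP 4.2.2 plans estimation and names no test, threshold or decision rule for safety. Excluding zero is used above only as a yardstick.
- Attempts are followed during the trial. Protocol 9.4.1 puts them in the safety reports as their own item, and protocol 9.4.2 gives the SMC monitoring data by masked group. That stands, but it is oversight and not the final reported contrast.
- Detail for each type may sit in the Analysis Implementation Plan, which is not among the documents. Protocol 9.5.2 extends similar analyses to the other outcome measures, among which Table 4 lists the three event types. That can be read as promising a contrast for each type, and SAP 4.2.2 does not carry it through.
- Pooling is a trade-off. With other events at 2% the loss is modest, and if all types rise together the pooled measure picks up harm more often.
- Separate analysis is no cure. In the assumed scenario it still misses the suicidal excess in 38% to 53% of trials, and several unadjusted intervals invite chance findings.

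**Conclusion.** The point holds in a limited form. The pooled measure is the only safety contrast for which the SAP specifies a difference and interval. An excess confined to suicidal events could therefore show in the by-arm tables, have no estimated contrast, and sit beside a pooled interval that includes zero.

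The size cannot be fixed from the documents. Under the assumed 3% versus 10%, pooling lowers detection from 47–62% to between 15–18% (other events 20%) and 38–50% (other events 2%). It raises detection to 61–74% if other events also go from 10% to 17%. These figures assume independent youth and, except in the last case, equal background in both arms.

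The documents do not support saying that a suicidal signal would be hidden or that the plan would declare the arms equally safe. This is a cheap improvement to analysis and reporting. It touches no clinical management rule.

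**What to change.** In SAP 4.2.2, for each of the three safety measures in SAP 3.2, add the by-arm proportion and the between-arm difference with a 95% CI. Show suicide attempts separately from ideation, and give event counts by arm. Keep the pooled measure as an overall summary, since it serves the case where all types rise together. Label the added estimates as unadjusted, and state that an interval including zero is not evidence of no harm.

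The cost is SAP wording and a few table rows. Protocol 7.2 already has these events entered on adverse event forms, and protocol 6.5 already has the number and dates of suicide attempts collected. The downside is wide intervals for rare events, attempts above all, and several unadjusted comparisons where there is now one.

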4.2.3 Missing and unscorable data

Loss-to-follow-up

In mental health research, there is concern about biased results due to loss to follow-up. For that reason, if more than 10% of participants are lost to follow-up before six months, or if a larger proportion of participants are lost to follow-up in one arm (especially if the loss is due to serious adverse events, or suicide attempts), analyses will be undertaken to explore the potential effects of missing data on the conclusions of the study. The characteristics at study entry (gender, age, mode of transmission, severity of mental health distress and viral load suppression status) for participants who discontinued from the study before six months will be compared between the TI-

CBT and Discussion Control arms. Characteristics of participants discontinuing vs. not discontinuing will be compared overall and within intervention and control arms. In addition, the reasons for losses to follow-up will be assessed and compared between intervention and control arms. The probability and timing of loss to follow-up will be summarized and compared between arms using Kaplan-Meier plots and the log-rank test.

Unscorable UCLA PTSD-RI assessments

The UCLA PTSD-RI instrument used to assess trauma symptoms features two parts: (1) endorsement of one or more past traumas; and (2) assessment of post-traumatic stress symptoms, from which a symptom score is derived. If trauma is not endorsed in the first part, the second part is skipped and no score is obtained although the survey is technically “completed.” We refer to such instances as “unscorable” assessments.

Unscorable assessments will be effectively treated as missing data. All primary and secondary objectives will be first conducted according to the complete case principle, wherein only youth with complete and scorable outcomes are included within analyses that include UCLA PTSD-RI scores. However, youth with unscorable assessments are likely to differ from those with scorable assessments, and these differences can bias treatment effect estimates. Restriction to complete cases also reduces sample size, and subsequently, power to detect a treatment effect. Imputation, or replacing unscorable data with a predicted score, can help with assessing the degree of bias within the complete case analysis and potentially improve power by allowing all youth to be included within analysis.

In what follows, missing refers to “unscorable.” There are three types of missing data. If scores are “missing completely at random” (MCAR), observed scores can be thought of as a simple random sample of all scores. That is, missing scores are not related to any other missing or observed scores or variables. On the other hand, if scores are “missing not at random” (MNAR), whether a score is missing depends on the value of the score itself. Analyses of MNAR data are complex and require correct specification of the relationship between missing and observed scores, which is unknowable. An intermediate situation is if scores are “missing at random” (MAR), where missingness is assumed to depend only on observed information, such as other scores or participant and site characteristics. If the MAR assumption holds, and missing scores are predicted (“imputed”) based on these observed factors, resulting analyses will be unbiased. Most analyses of missing data assume MAR.

MCAR is the only missingness assumption that can be assessed using the data. A missing indicator is constructed for each participant, equal to 1 if their survey was unscorable and 0 otherwise. If MCAR holds, all other variables should be approximately balanced between groups defined by the missing indicator. We will assess associations descriptively and formally using hypothesis testing within the ITT population only. Complete case analysis (CCA), which excludes youth with missing data, will be reported regardless of results. If investigation provides evidence that MCAR holds, the CCA will provide unbiased effect estimates. However, it is rare that data are truly MCAR.

If investigation provides evidence that the data is not MCAR, MAR will be assumed and imputation will be performed for the ITT analysis population. The set of variables used for

imputation will be informed by the analysis model and identified associations between missing indicators and observed variable, and finalized with input from the protocol team. Imputation will replace missing scores using predictions based on these variables. For example, UCLA PTSD-RI score may be predicted using PHQ-9 score, GAD-7 score, and site. To account for uncertainty in predicted values, multiple imputations will be performed. Analysis will be repeated for each imputed data set, and results averaged. Variance estimates will be obtained by applying “Rubin’s Rules.” Correlation among youth in the same group, or “clustering,” will also be incorporated into imputation models.

5 Report Contents

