### 6.3.6 Youth Randomized Trial: 6 Month Follow-up Study Visit

The 6 Month Follow-up Study Visit is targeted to take place on Day 182, counted from the day of the first group session as Day 0, with a targeted window of  $\pm 14$  days and an allowable window of  $\pm 30$  days.

Youth 6 Month Follow-up Study Visit Procedures for Randomized Trial ( $\pm 30$ days)		
Clinical		
 
Obtain targeted medical/medications history per Section 6.5
 

Behavioral and Counseling		
 
Administer electronic questionnaires - pen and paper may be substituted per Section 10.1:               
 
PHQ-9
 
GAD-7
 
UCLA PTSD exposure screener and reaction index
 
Self-report ART Adherence
 
Barriers to adherence
 
Gender-based Violence (WHO – Victim/Perpetrator)
 
Gender Roles (Rachel Jewkes)
 
AIDS-Related Stigma Scale
 
AIDS Risk Behavior Assessment (Sexual behavior/Drug and alcohol use)
 
Children’s Report of Parenting Behavior Inventory
 
Risk for Contamination
 
 
 

Laboratory	Blood	
 
Collect blood for:               
 
HIV-1 RNA (viral load test)
 
Plasma for Inflammatory biomarkers
 
 
 
Hair sample (50-60 strands) for ART concentration – to be collected from the head (scalp) only; not required if participant is bald
 

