4.2 Analysis Approaches

4.2.1 Analysis of the Primary Objective

The primary efficacy analysis will compare all primary outcome measures between randomized arms using the ITT analysis population. The primary outcome measures will be analyzed using a two-sided type I error rate of 0.05 and associated 95% confidence intervals in comparing differences between randomized arms. There will be no statistical adjustment for multiple comparisons. Only complete cases, i.e., youth with data for a specified measure, will be analyzed.

It is expected that the three mental health measures (PHQ-9, GAD-7, UCLA PTSD-RI) will be correlated; they will therefore be analyzed jointly using a composite measure. The three measures will first be standardized to the same scale, with mean 0 and standard deviation 1. Standardization will be done for each measure by subtracting the baseline (Pre-Entry) overall variable mean from each observation and dividing by the baseline pooled sample standard deviation. Resulting standardized scores thus represent the number of standard deviations from the baseline mean. Internal consistency of the mental health composite will be checked by examining Cronbach's alpha for the three standardized mental health measures to see if they form a coherent measure, indicated by an alpha greater than or equal to 0.70. If coherent, the composite mental health score will be created by summing the standardized scores within-youth.

The primary analysis comparing the composite mental health measure between arms will be a group-level analysis. One valid method for analyzing intervention effects within cluster randomized trials is to compute the mean for each cluster and then perform a t-test on the cluster-specific summaries. Here, a paired t-test will be performed for the difference in means between arms, with pairs defined by each distinct combination of site and wave. The same procedure will be used to analyze each mental health measure separately.

Supplementary Analyses

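### SAP 4.2.3 makes imputation depend on evidence against MCAR and limits it to unscorable UCLA scores, so no specified analysis re-estimates the effect with lost youth included, and the re-estimate for unscorable youth may not be run

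*SAP*

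**What the plan says.** - **Primary analysis set (SAP 4.2.1).** "Only complete cases, i.e., youth with data for a specified measure, will be analyzed". This applies to each of the four primary measures: PHQ-9, GAD-7, UCLA PTSD-RI and the composite.
- **How a UCLA score is lost (SAP 4.2.3).** "If trauma is not endorsed in the first part, the second part is skipped and no score is obtained". Protocol 6.3.6 lists the "UCLA PTSD exposure screener and reaction index" at the 6-month visit, which is the primary time point.
- **Scope of the imputation text (SAP 4.2.3).** It opens with "In what follows, missing refers to" and then the single word unscorable. The missing-data indicator is 1 for an unscorable survey and 0 otherwise.
- **The condition (SAP 4.2.3).** "We will assess associations descriptively and formally using hypothesis testing within the ITT population only". Then "If investigation provides evidence that MCAR holds, the CCA will provide unbiased effect estimates", but "If investigation provides evidence that the data is not MCAR, MAR will be assumed and imputation will be performed for the ITT analysis population". No significance level, variable list or decision rule is stated.
- **The same analysis elsewhere.** The supplementary analyses in SAP 4.2.1 say the primary analyses will be repeated with imputed data. SAP 5.2.6 lists effects by complete-case and imputed strategy. Neither states a condition.
- **Two-component composite (SAP 4.2.1).** PHQ-9 plus GAD-7 is analysed only if more than 10% of UCLA assessments are unscorable.
- **Loss to follow-up (SAP 4.2.3).** If loss exceeds 10% or is larger in one arm, analyses will explore what missing data could do to the conclusions. Those named are comparisons of entry characteristics, comparisons of reasons, Kaplan-Meier plots and a log-rank test.

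**The concern.** Three features combine.

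1. Finding no evidence against MCAR is treated as support for an unbiased complete-case result. With few unscorable youth it may only reflect low power. The SAP itself expects unscorable youth to differ from the others and calls true MCAR rare, so the condition sits oddly with its own reasoning.
2. Youth with no 6-month assessment are outside the imputation, and no other specified analysis brings them back into an effect estimate.
3. Whether a youth contributes to the UCLA and composite outcomes depends on an answer given after randomization. If that answer differs by arm, the complete-case comparison is no longer protected by randomization, although the analysis is labelled ITT.

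At stake is whether readers of the primary report will see how far the UCLA and composite results depend on who was left out.

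**Working it through.** **Reference figure.** The plan's detectable difference uses SE = √(2·(1+(n−1)·ICC)/(m·n)) and a noncentral t with 2(m−1) df, at 80% power and two-sided 0.05.
- m=16, n=8, ICC 0.05: SE = √(2·1.35/128) = 0.145, detectable 0.42 SD.
- m=12, n=8, ICC 0.15: SE = √(2·2.05/96) = 0.207, detectable 0.61 SD.

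This reproduces all 36 cells of Protocol Table 5. The text gives 0.42 to 0.62.

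**Which paths lead to a re-estimate?**

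| Situation at 6 months | Imputed effect | PHQ-9 + GAD-7 composite |
|---|---|---|
| Unscorable, evidence against MCAR | yes | only if >10% unscorable |
| Unscorable, no such evidence, >10% | no | yes, but without UCLA |
| Unscorable, no such evidence, ≤10% | no | no |
| No 6-month assessment | not specified | does not restore them |

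The multi-level model in SAP 4.2.1 nests individuals in groups. It is not described as a repeated-measures model, so it does not recover lost youth through earlier visits.

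**How informative is a non-significant test?** The rates and gaps here are assumptions. For one covariate, SE = √(1/n₁+1/n₂). With 192 youth and 10% unscorable (19.2 versus 172.8), SE = 0.241. A 0.5 SD difference gives 0.5/0.241 = 2.08, so power is Φ(2.08−1.96) ≈ 55%. The same calculation gives 67% for 256 youth, and 33 to 41% if 5% are unscorable. For a 0.4 SD difference after 10% loss, noncentral-t power is 44% (23 versus 207) and 34% (17 versus 156).

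**Several variables tested together.** The SAP check covers variables generally, so single-covariate power understates how often it triggers. The simulation drew three scores with correlation 0.6. Unscorability was logistic in the PTSD score (slope 0.5 or 1.0). Arm, PHQ-9 and GAD-7 were each tested at 5%, with N = 200.
- 7% versus 13%, or 5% versus 15%, unscorable by arm: condition met in about 50 to 88% of trials.
- 10% versus 30%: met in about 97 to 99%.

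**Bias from unscorable scores.** If scorable and unscorable youth differ by D in both arms, the complete-case arm difference is shifted by D·(p_T−p_C). With D = 0.4 to 0.7 composite SD:
- 13% versus 7%: 0.06×0.4 = 0.024 to 0.06×0.7 = 0.042. The simulation gives 0.03 to 0.04.
- 15% versus 5%: 0.10×0.4 = 0.04 to 0.10×0.7 = 0.07. The simulation gives 0.04 to 0.07.

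Relative to 0.42 SD, this is 0.03/0.42 = 7% to 0.07/0.42 = 17%. The sign follows p_T−p_C. If unscorable youth are less symptomatic, a higher share in control favours TI-CBT, and a higher share in TI-CBT works against it.

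**Loss to follow-up.** At 10% loss, 0.10×192 ≈ 19 to 0.10×256 ≈ 26 youth are left out. Suppose TI-CBT dropouts differ from completers by 0.5 to 1.0 SD and control dropouts do not. The shift is then 0.10×0.5 = 0.05 to 0.10×1.0 = 0.10 SD.

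**The case against.** The defence has real force on several points.

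- **The condition is not a single test.** It is a descriptive and formal investigation across variables, and the SAP plainly expects MCAR to fail. A reader might infer from 34 to 44% power that imputation would usually be skipped when bias exists. The documents do not support that. If arm is among the variables tested, the condition is usually met when the arms differ enough to cause bias. When the shares are equal by arm it is met less often, but with a common gap D equal shares produce no arm bias.
- **A large unscorable imbalance would be caught.** At 10% versus 30% the bias is 0.08 to 0.14 SD. But the condition is then met almost always, and with 20% unscorable overall the two-component composite also runs. Those bias figures cannot be paired with the low power figures, which assume 10% unscorable.
- **Unscorable youth do not leave the primary analysis altogether.** They stay in the PHQ-9 and GAD-7 comparisons.
- **The direction is unknown.** A reader might infer that the bias favours TI-CBT. If the program led youth to stop endorsing trauma, it would run against TI-CBT. The documents do not show that endorsement changes at all.
- **Not wholly unexamined.** SAP 5.2.6 reports baseline characteristics of scorable and unscorable youth. The loss-to-follow-up commitment is broad enough to permit a re-estimate.

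These points limit the size of the concern but do not remove it. No decision rule is given, SAP 4.2.1 and 4.2.3 disagree on whether the imputed analysis is conditional, and permission to explore dropout is not a specified estimator.

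**Conclusion.** The concern holds in a limited form. Imputation is conditional on an undefined finding and restricted to unscorable UCLA scores. That conflicts with SAP 4.2.1 and 5.2.6, and with the SAP's own view that unscorable youth probably differ. When 10% or fewer are unscorable and the condition is not met, neither the UCLA nor the composite effect is re-estimated. For youth lost before 6 months, no specified analysis re-estimates any of the four primary measures.

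The likely size is modest. Unscorable scores shift the composite by about 0.03 to 0.07 SD at 7% versus 13% or 5% versus 15% by arm, and the condition would miss this in roughly 10 to 50% of trials if arm, PHQ-9 and GAD-7 are tested. One-sided informative dropout at 10% loss gives 0.05 to 0.10 SD. The rates by arm, score gaps, between-scale correlation and set of tested variables are assumptions; only the 10% loss is a planning figure in the documents. The defect lies in the supplementary analyses; the primary estimator is not in question.

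**What to change.** 1. Delete the MCAR condition from SAP 4.2.3 so that it agrees with 4.2.1 and 5.2.6. The comparison of scorable and unscorable youth can stay as description.
2. Always run the cluster-aware multiple imputation with Rubin's rules that 4.2.3 already describes, as a sensitivity analysis for the composite and each scale. Cover both unscorable UCLA scores and youth with no 6-month assessment. Put arm, site, wave, group, screening scores and IPL scores in the model.
3. Report the unscorable share by arm at 6 months.

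Optional additions are a bound with unscorable UCLA set to the lowest score, and the PHQ-9 + GAD-7 composite reported whatever the unscorable share. The bound has some value because imputation under MAR removes only part of the bias if unscorability depends on the UCLA score itself, and the SAP plans no MNAR analysis.

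The cost is SAP wording, modest programming and a few more sensitivity results to report. The complete-case primary analysis stays as it is.

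### UCLA PTSD-RI scores for youth who endorsed no trauma are imputed from youth who did, and no planned analysis varies the missing-at-random assumption

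*SAP*

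**What the plan says.** SAP 4.2.3 describes the UCLA PTSD-RI as having two parts: "If trauma is not endorsed in the first part, the second part is skipped and no score is obtained". It then states: "Unscorable assessments will be effectively treated as missing data". It accepts that unscorable youth probably differ from scorable youth and that this can bias the treatment effect.

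The complete-case analysis comes first. Imputation is offered because it "can help with assessing the degree of bias within the complete case analysis". The rule for using it is: "If investigation provides evidence that the data is not MCAR, MAR will be assumed and imputation will be performed for the ITT analysis population". The example model is: "For example, UCLA PTSD-RI score may be predicted using PHQ-9 score, GAD-7 score, and site". The predictor list is to be informed by the analysis model and by what is associated with missingness, and then "finalized with input from the protocol team". Multiple imputation, Rubin's Rules and clustering are specified.

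Missing not at random (MNAR) is set aside: "Analyses of MNAR data are complex and require correct specification of the relationship between missing and observed scores, which is unknowable". SAP 5.2.6 accordingly lists UCLA treatment effects under two strategies only, complete case and imputed.

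SAP 3.1 makes the 6-month UCLA score a primary outcome in its own right and one of three components of the composite. SAP 4.2.1 adds a PHQ-9/GAD-7 composite if more than 10% of UCLA forms are unscorable. Protocol 5.5.1 gives the UCLA score a range of 0 to 51.

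**The concern.** The cause of an unscorable form is known and recorded: the youth endorsed no trauma. At a given visit every youth with a score endorsed trauma, and no youth without a score for this reason did. The two sets do not overlap on the variable that decides missingness. A regression fitted on endorsers gives each non-endorser the symptom level of an endorser with similar predictor values. Whether that level is right cannot be checked at that visit.

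The imputation is meant to show how biased the complete-case result is. But both results draw their UCLA information from the same endorsers, so they can agree whether or not bias is present. A reader of the primary report could take that agreement as robustness of a primary outcome. Endorsement at 6 months is recorded after randomization, so the unscorable rate could differ by arm.

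**Working it through.** **Step 1: the plan's own scale.** The documents give no figure for imputation bias. Their effect-size scale comes from Protocol Table 5. With m groups per arm of n youth, SE = sqrt(2(1 + (n-1)ICC)/(mn)), and a noncentral t with 2(m-1) degrees of freedom:
- m = 16, n = 8, ICC 0.05: SE = sqrt(2 x 1.35/128) = 0.145; detectable difference 0.421 (Table 5: 0.42).
- m = 12, n = 8, ICC 0.15: SE = sqrt(2 x 2.05/96) = 0.207; detectable difference 0.606 (Table 5: 0.61).

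The table reproduces. It is used here only to judge size.

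**Step 2: what the documents give on correlation.** SAP 4.2.1 says only that the three measures should correlate, and calls the composite coherent at Cronbach's alpha of 0.70 or more. For three standardized items with common correlation r, alpha = 3r/(1+2r), so r = alpha/(3 - 2 alpha). At 0.70, r = 0.70/1.60 = 0.4375. All other values of r below are assumptions.

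**Step 3: share of complete-case bias left after imputation.** Suppose being unscorable follows the UCLA score itself, rates differ by arm and arm is in the model. Imputation then recovers roughly the part of the shift that PHQ-9 and GAD-7 explain. The share left is 1 - R², with R² = 2r²/(1+r). A large simulation (400,000 per arm, true shift 0.42 SD) checks this:

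| r | alpha | R² | 1 - R² | simulated share left |
|---|---|---|---|---|
| 0.30 | 0.56 | 0.14 | 86% | about 89% |
| 0.4375 | 0.70 | 0.27 | 73% | 78% |
| 0.50 | 0.75 | 0.33 | 67% | 71-72% |
| 0.60 | 0.82 | 0.45 | 55% | 61% |
| 0.75 | 0.90 | 0.64 | 36% | 42% |

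**Step 4: other conditions.**
- MAR true, arm in the model: about 0% left.
- MAR true, arm omitted, unequal rates: 9-137% left.
- Score-driven missingness, arm omitted: 42-129% left.
- Unscorable youth fixed 2 SD below the baseline mean, arm in the model: 53-100% left.
- Equal rates with score-driven missingness: complete-case bias in the arm difference is about 0, so no share is defined. Omitting arm then creates a bias of about 0.02-0.05 SD.

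**Step 5: size in SD.** Assume r = 0.55, no treatment effect, score-driven missingness and arm in the model. At 15% v 25% unscorable (TI-CBT v control), the complete-case bias is -0.06 to -0.10 SD and the imputed bias -0.04 to -0.07 SD. At 10% v 30% they are -0.13 to -0.21 and -0.09 to -0.14 SD. All these rates are assumed. Reversing the arms reverses the sign.

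**Step 6: what a delta analysis would show.** Shift the imputed scores by delta_T and delta_C. The arm difference then moves by about p_T x delta_T - p_C x delta_C, where p is the unscorable proportion. A common shift of -1 SD at 15% v 25% moves it by -0.15 + 0.25 = +0.10 SD; at 10% v 30%, by +0.20 SD. With 20% in both arms a common shift moves nothing, but -1 SD in control alone moves it by +0.20 SD. Delta must therefore be free to differ by arm.

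**The case against.** **The predictors are only an example.** This is correct. The SAP leaves the list open, so arm, group and an earlier UCLA score are not excluded. They are not required either. Step 4 shows that leaving arm out can do harm even when MAR holds. An earlier UCLA score helps only youth who have one.

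**A two-component composite is already planned.** This stands for the composite: above 10% unscorable, the PHQ-9/GAD-7 version avoids UCLA altogether. Imputed bias on the three-component composite is also small, 0.01-0.08 SD in simulations on assumptions like those in Step 5. Neither addresses the UCLA score as a primary outcome.

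**Some by-arm reporting exists.** SAP 4.1 and 5.2.4 give the N behind UCLA scores by arm, and the missingness checks could include arm. But that N mixes loss to follow-up with unscorable forms, and SAP 5.2.6 compares scorable with unscorable youth without asking for this within arm. Tables in the Analysis Implementation Plan may add detail that is not visible here.

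**Stronger readings that the documents do not support.** A reader might infer that imputation leaves a set share of the bias, such as 70%. That figure needs an assumed correlation, score-driven missingness and unequal rates. A reader might also infer that the direction is known, with non-endorsers low in symptoms and the bias favouring TI-CBT. The SAP says only that these youth probably differ. A youth who endorsed trauma earlier and not at 6 months has changed a report, which need not mean few symptoms, and TI-CBT could raise or lower endorsement. For the same reason, the range from the MAR prediction down to 0 need not contain the truth.

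**Conclusion.** The point holds as a gap in the sensitivity analyses. At each visit the imputation extrapolates from endorsers to non-endorsers, and no planned analysis varies the assumption that makes this valid. Agreement between the complete-case and imputed UCLA results is therefore weak evidence against bias.

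The amount of bias left is not fixed by the documents. It is about none if MAR holds with arm in the model. It is roughly 60-80% of the complete-case bias if missingness follows the score, unscorable rates differ by arm, arm is in the model and r is about 0.44-0.60. In the assumed scenarios of Step 5 that is 0.04-0.14 SD, against the 0.42-0.62 SD the trial is powered to detect.

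The SAP is right that the MNAR mechanism cannot be known. That does not prevent varying it over a stated range, and the scale has a floor of 0. This is a cheap improvement and does not invalidate the primary analysis.

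**What to change.** In SAP 4.2.3:

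1. Require arm, group and the youth's earlier UCLA score (Screening or IPL, where one exists) in the imputation model, alongside PHQ-9 and GAD-7.
2. Add a delta-adjusted sensitivity analysis for unscorable youth, with delta allowed to differ by arm. Run it from the MAR prediction down to the scale floor of 0, and add upward shifts for youth who endorsed trauma at an earlier visit. Report the delta at which the conclusion changes.
3. Report the unscorable proportion by arm, separately from loss to follow-up, and compare scorable with unscorable youth within arm. Amend SAP 5.2.6 to match.

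The cost is SAP wording and a few extra runs of an imputation already planned. The UCLA result becomes a range instead of one figure. The change is best made before outcome results by arm are seen.
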